9 STATISTICAL CONSIDERATIONS

9.1 General Statistical Considerations

The investigation will have two primary analyses, one regarding Adaptive speech in noise between Baha 6 Max SP and unaided hearing ($\alpha = 0.005$) and one regarding preference between Baha 6 Max SP and Baha 5 SP ($\alpha = 0.045$). These endpoints will be evaluated using the decision rules of the Holm's test. (Ref NEJM2). With these procedures we will have a total type I error <0.05 .

For the comparison between the Baha 6 Max SP and unaided the design don't take care of period effect so the statistical analyses will be paired. For the comparison between Baha 6 Max SP and Baha 5 SP a cross over design was applied and the statistical analyses will be adjusted for period effect.

The main results for all outcome variables are the estimate of mean differences with 95% confidence interval (CI) with a descriptive p-value. The p-value will only have a confirmatory value for the two primary analyses.

For comparison between the Baha 6 Max SP and unaided Fisher's non-parametric permutation test for paired observations will be used for continuous variables and Sign test for dichotomous variables and ordered categorical variables.

For the comparison between Baha 6 Max SP and Baha 5 SP the following period adjusted analysis should be performed for continuous variables: For each subject take the difference between the measurement in second period and the measurement in first period. Then analyse these differences between the subjects randomised to Baha 6 Max SP in the first period and the subjects randomised to Baha 5 SP in the first period with Fisher's two-sided non-parametric permutation test. The Fisher's permutation test is preferable because it is non-parametric and gives consistent 95% CI.

For the comparison between Baha 6 Max SP and Baha 5 SP the following period adjusted analysis should be performed for dichotomous and ordered categorical variables: For each subject take the difference as, improved no change and worsened, between the measurement in second period and the measurement in first period. Then analyse these ordered categorical differences between the subjects randomised to Baha 6 Max SP in the first period and the subjects randomised to Baha 5 SP in the first period with Mantel-Haenszel chi-square test.

For comparison of preference of device between Baha 6 Max SP and Baha 5 SP the Sign test will be used.

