9.3 Hypotheses

9.3.1 Primary Hypothesis

The first primary efficacy analysis is the comparison regarding adaptive speech in noise [signal-to-noise ratio, 50% speech understanding] between Baha 6 Max SP and unaided using a two-sided Fisher's non-parametric permutation test for paired observations on significance level 0.005.

$$H_0: \mu_{\text{Baha 6 Max SP}} = \mu_{\text{unaided}}$$

$$H_1: \mu_{\text{Baha 6 Max SP}} > \mu_{\text{unaided}} \text{ or } \mu_{\text{Baha 6 SP}} < \mu_{\text{unaided}}$$

The second primary efficacy analysis is the comparison regarding preference of device between Baha 6 Max SP and unaided using a two-sided Sign test on significance level 0.045.

H_0 : Probability preference of Baha 6 Max SP before Baha 5 SP = 0.5, given preferred any.

H_1 : Probability preference of Baha 6 Max SP before Baha 5 SP > 0.5, given preferred any or Probability preference of Baha 6 Max SP before Baha 5 SP < 0.5, given preferred any.

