9.6 Primary Endpoint Analyses

The first primary endpoint analysis will be the comparison of adaptive speech in noise [signal-to-noise ratio, 50% speech understanding] between the Baha 6 Max SP and unaided with two-sided Fisher's non-parametric permutation test for paired observations on significance level 0.005 on the FAS population. Mean difference with 99.5% confidence interval will be given together with the distribution of the difference.

The second primary endpoint analysis will be the comparison between Baha 6 Max SP and Baha 5 SP regarding preference of device with two-sided Sign test on significance level. Proportion of preferences for Baha 6 Max SP with exact 95 % CI will be calculated.

If one of the two primary efficacy analyses are significant but not the other, the other can be retested at the 5% significance level according to the decision rule of the Holms test (9).

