3 STUDY ENDPOINTS

3.1 Endpoints to be used for the primary objectives

- First primary objective: Adaptive speech in noise [signal-to-noise ratio, 50% speech understanding]
- Second primary objective: Preference of device.

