3.2 Endpoints to be used for the secondary objectives

- Daily use of sound processors (hours) from Diary, Only Baha 6 Max SP vs Baha 5 SP
- Change of battery from Diary, Only Baha 6 Max SP vs Baha 5 SP
- Switch to their own sound processor and the reason for change from Diary (Only Baha 6 Max SP vs Baha 5 SP)
- Adaptive speech in noise [signal-to-noise ratio, 50% speech understanding] Baha 6 Max SP and Baha 5 SP
- Thresholds audiology, sound-field [0.25, 0.5, 1.0, 2.0, 3.0, 4.0, 6.0, 8.0 9.0 and 10.0 kHz]
- Speech in quiet [% correctly perceived words at 65dB SPL]
- Evaluation of sound quality and listening effort through sound clips. Only Baha 6 Max SP and Baha 5 SP.

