4.2 Analyses

4.2.1 Pass/Fail Criteria

If the signal-to-noise-ratio for a subject is at least 50% regarding speech understanding the subject will be classified as a responder. The primary objective of the study is that the null-hypothesis that the proportion of responders for the Baha 6 Max SP and the Baha 5 SP are equal.

If the two-sided p-value when testing the hypothesis above is below 5% the results of the study are considered successful.

This means that the pass/fail criteria for each subject is speech understanding and the pass-criteria is that the signal-to-noise-ratio for a subject is at least 50%.

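### SAP 4.2.1 decides study success by one Baha 6 Max versus Baha 5 responder test at 5%, which is neither protocol primary, and drops the 0.005/0.045 split and the Holm rule

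*SAP*

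**What the plan says.** **Protocol.** Section 9.3.1 tests speech in noise for Baha 6 Max against unaided with a two-sided "permutation test for paired observations on significance level 0.005". It tests preference "using a two-sided Sign test on significance level 0.045", with hypotheses stated for Baha 6 Max against Baha 5. Section 9.6 adds that if only one of the two is significant, "the other can be retested at the 5% significance level according to the decision rule of the Holms test". Section 9.1 says of this scheme: "With these procedures we will have a total type I error <0.05". On everything else it says: "The p-value will only have a confirmatory value for the two primary analyses". Section 9.2.2 lists speech in noise against Baha 5 as a secondary endpoint.

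**SAP.** Section 4.2.1 defines a responder from the speech-in-noise result and takes as the primary objective the null hypothesis of equal responder proportions for the two processors. It then states: "If the two-sided p-value when testing the hypothesis above is below 5% the results of the study are considered successful". Section 4.2.2 repeats that hypothesis as the first primary and keeps preference as the second, both by a binomial test, with no significance level for either. Section 3.1 also has "Second primary objective: Preference of device". Yet section 3.2 places this among the secondary endpoints: "Adaptive speech in noise [signal-to-noise ratio, 50% speech understanding] Baha 6 Max SP and Baha 5 SP". Neither 0.045 nor Holm appears anywhere in the SAP. The value 0.0050 appears once, in the sample-size text that section 4.1 carries over from the protocol.

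**The concern.** Endpoint, comparator, test and level of the deciding analysis all differ between the two documents. The protocol's design rationale (7.1.1) ties the unaided comparison to regulatory approval, but no part of SAP 4.2 tests it. Preference is still called primary in the SAP but has no level and no part in the success rule.

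Two things are at stake. First, the verdict on a pivotal study could rest on a comparison whose p-value the protocol treats as descriptive, whatever happens on the two primaries. Second, the familywise control promised in protocol 9.1 is no longer specified for the two analyses that the SAP itself calls primary.

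**Working it through.** **1. The protocol's own error figure.** Inputs: 0.005 and 0.045 (protocol 9.3.1).

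- If both nulls are true, the bound is 0.005 + 0.045 = 0.050. Under independence it is 1 − 0.995 × 0.955 = 0.0498.
- If one null is true, the retest uses at most 0.05.

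The overall 5% control in protocol 9.1 is reproduced.

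**2. The two decision rules side by side.**

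| | Protocol 9.1, 9.3.1, 9.6 | SAP 4.2.1, 4.2.2 |
|---|---|---|
| First primary | Mean SNR, Baha 6 Max vs unaided | Responder proportion, Baha 6 Max vs Baha 5 |
| Test and level | Paired permutation test, 0.005 | Binomial test, 5% |
| Second primary | Preference vs Baha 5, sign test, 0.045 | Preference vs Baha 5, binomial test, no level |
| Link between them | Holm retest at 0.05 | None |
| Basis for success | The two primaries | The responder test alone |

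The 5% in the Holm rule does not support the SAP. It applies only after one primary has succeeded, and only to the other protocol primary. The version difference does not explain the change either: the SAP is based on protocol version 3.0, and the change history lists only section 8.4 for version 4.0.

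**3. Error rate under the SAP.** The single success declaration has error of at most 5%. Suppose preference were also claimed at 5%, which is an assumption because the SAP states no level:

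- Nominal, independent: 1 − 0.95² = 0.0975. Upper bound: 0.05 + 0.05 = 0.10.
- Exact two-sided binomial tests, independent, with the same number of informative pairs in each: 1 − (1 − size)².

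| Informative pairs | Size of one test | Joint error |
|---|---|---|
| 6 | 0.03125 | 0.0615 |
| 9 | 0.03906 | 0.0766 |
| 12 | 0.03857 | 0.0757 |
| 15 | 0.03516 | 0.0691 |
| 16 | 0.02127 | 0.0421 |

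With equal numbers of pairs, 6, 9, 12 and 15 are the only counts up to 16 at which the joint error exceeds 5%. The maximum over all combinations up to 16 is 0.0766, at 9 and 9.

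**4. Can the deciding test succeed?** Only subjects who are responders on one device and not the other count. With 5 such subjects the smallest two-sided p is 2 × 0.5⁵ = 0.0625. So with 5 or fewer discordant pairs the SAP's success criterion cannot be met, however large the benefit over unaided.

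**5. Power if the protocol's rule is restored.** Inputs: mean difference 16 dB, SD 12.5, 15 subjects; 86% preference, 16 subjects (protocol 9.4).

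- First primary: standardised difference 16/12.5 = 1.28. A paired t-test at two-sided 0.005 has power 0.892 at n = 14, 0.924 at n = 15 and 0.947 at n = 16. Simulated permutation tests at n = 15 give 0.91 to 0.92. The stated 15 subjects for 90% power are reproduced.
- Preference: at n = 16 the exact sign test rejects at 13 or more, or 3 or fewer. The two-sided p is 0.0213 at 13 and 0.0768 at 12. Power at 86% is 0.824, against the stated 80%.
- Using 0.045 rather than 0.05: the exact rejection region is the same at both levels for every n up to 16.

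**The case against.** The case on the other side has five parts.

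- **A single test at 5% inflates nothing, and the joint-error figures are hypothetical.** This stands. They need an assumed level for preference, independence within the same subjects and an exact binomial test, which the SAP does not specify. At 16 informative pairs the result is below 5%. The concern rests on the contradiction, not on these figures.
- **Spurious success is unlikely.** The Matrix test (protocol 7.3.3) adapts the speech level until understanding is 50%, so on one reading every subject is a responder on both devices and nothing is discordant. Read literally, an SNR in dB cannot be compared with 50%. This is a fair point, but it makes an unmeetable or undecidable criterion the likelier harm, which is a further reason to replace it.
- **The protocol has no study-level success rule.** Correct: it does not say whether one or both primaries must be met. Stating success per objective fits a Holm procedure but is a recommendation here. The SAP rule still uses neither primary.
- **The SAP is a companion document, so its silence could leave the protocol's rule in force.** That might cover the missing Holm statement in 4.2.2. It cannot cover 4.2.1, which states a conflicting rule. SAP section 1 also requires departures from the SAP to be reported, so running the protocol's tests would itself count as a deviation.
- **The protocol text has slips of its own.** The sentence in 9.3.1 that introduces the preference test names unaided as comparator, although its hypotheses name Baha 5, and 9.6 omits the preference level. Both stand and should not be copied.

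**Conclusion.** The concern holds. SAP 4.2.1 is wrong as written: it gives the success decision to a comparison that both documents class as secondary, in a responder form the protocol does not define, at a level the protocol did not allot to it. It leaves both protocol primaries out of that decision. The contradiction is established from the text alone and needs no assumption.

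The effect on type I error is conditional. It is at most 5% for the SAP's single declaration. It is nominally 9.75% (at most 10%) if preference is also claimed at 5%, or 4.2% at 16 informative pairs and at most 7.7% with independent exact binomial tests. The larger consequence is that the study's verdict may not correspond to either hypothesis for which it was sized. This must be fixed.

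**What to change.** Replace SAP 4.2.1 and 4.2.2 with the protocol's hypotheses and decision rule:

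1. Mean speech-in-noise SNR, Baha 6 Max vs unaided: paired permutation test, two-sided 0.005.
2. Preference, Baha 6 Max vs Baha 5: sign test, two-sided 0.045.
3. If exactly one is significant, retest the other at 0.05.
4. State success separately for each primary objective.
5. Label all other p-values descriptive, including speech in noise vs Baha 5.

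Name Baha 5 explicitly as the preference comparator, and correct the slips in protocol 9.3.1 and 9.6 at the same time. If the change of rule was deliberate, it needs a documented justification and a matching protocol amendment.

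The cost is a rewrite of two SAP subsections. No subjects are added: on the protocol's assumptions, power is about 92% at 15 subjects for the first primary. For preference it is 82% at 16, provided every subject states a preference. Using 0.045 rather than 0.05 costs preference nothing at any n up to 16.

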4.2.2 Primary Hypothesis

The first primary efficacy objective is the comparison regarding adaptive speech in noise. If the signal-to-noise-ratio for a subject is at least 50% regarding speech understanding the subject will be classified as a responder. The null-hypothesis that the proportion of responders for the Baha 6 Max SP and the Baha 5 SP are equal will be tested using the Binomial test.

The second primary efficacy analysis is to test the null-hypothesis that the proportion of subjects who prefer Baha 6 Max SP and the proportion of subjects who prefer Baha 5 SP are equal will be tested using the Binomial test.

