6 OBJECTIVES AND ENDPOINTS

Primary Objectives	Primary Endpoints

To compare hearing performance of speech in noise between Baha 6 Max SP and the unaided hearing (superiority).
 
To compare the preference of device between Baha 6 Max SP and Baha 5 SP
	
Adaptive speech in noise [signal-to-noise ratio, 50% speech understanding]
 
Preference of device

Secondary Objectives	Secondary Endpoints

To compare hearing performance between Baha 6 Max SP and Baha 5 SP in a home/normal environment hearing environment
	
 • Diary 
 ◦ Daily use of the SP (hours) ◦ Change of battery ◦ Switch to their own SP and reason for change

To compare hearing performance between Baha 6 Max SP and Baha 5 SP.
	
 • Adaptive speech in noise [signal-to-noise ratio, 50% speech understanding] • Thresholds audiology, sound-field [0.25, 0.5, 1.0, 2.0, 3.0, 4.0, 6.0, 8.0, 9.0 and 10.0 kHz] • Speech in quiet [% correctly perceived words at 65dB SPL] • Evaluation of sound quality and listening effort through sound clips

To compare hearing performance between Baha 6 Max SP and unaided.
	
 • Thresholds audiology, sound-field [0.25, 0.5, 1.0, 2.0, 3.0, 4.0, 6.0 and 8.0 kHz] • Speech in quiet [% correctly perceived words at 65dB SPL]
Safety Objective	Safety Outcome measures
Adverse events (AEs)	Information will be collected from Visit 1 and onwards.
Device deficiency (DDs)	Information will be collected from Visit 1 and onwards.

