7.1.1 Design Rationale

The primary purpose with this investigation is to test the Baha 6 Max SP versus unaided hearing in order to achieve regulatory approval and to investigate which device (Baha 6 Max versus Baha 5) the subjects prefer.

The second primary objective is to compare hearing performance between Baha 6 Max SP and Baha 5 SP in a home (normal) hearing environment. The subjects will test the two SPs during a week at home in a cross-over design (randomised test order). Based on their experiences with the SPs the subject will be asked which of them they prefer. Because all subjects are prescribed and used to amplified sound through bone conduction, one weeks testing at home is regarded as sufficient time to evaluate the performance of a SP. The investigation must be performed in an open fashion since it is not possible to blind the investigation due to differences in design.

After fitting of the test device several listening tests (adaptive speech in noise, thresholds audiometry and speech in quiet) will be performed in a sound booth.

The evaluation of sound quality and listening effort through sound clips (visit 3) will be performed in a blinded fashion, i.e. the subject will not know which SP that is tested. The test order will be randomised

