4 STATISTICS

4.1 Sample Size

In order to meet the sample sizes calculations for both primary analyses, 16 subjects will be included.

As this is an internal Cochlear investigation, patients will be recruited until the number of required patients are enrolled. Hence, no dropouts are expected.

First primary analysis: Baha 6 Max SP vs unaided regard Adaptive speech in noise

From the CIP: Assuming an individual mean difference (aided Baha 6 Max SP minus unaided) in speech recognition in noise of 16 dB SNR with a standard deviation (SD) of 12.5 (Busch et al, 2015),

a total sample of 15 eligible subjects are required to provide 90% power to reject the null hypothesis for the statistical test for the primary objective (change in dB SNR) using a two sided, alpha 0.0050, with Two-sided Fisher's non-parametric permutation test for paired observations.

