4.2.3 Secondary Hypotheses

For continuous variables and ordered categorical variables the Wilcoxon signed rank test will be applied and for binary variables the Binomial test will be applied when testing the null-hypothesis that the Baha 6 Max SP and the Baha 5 SP are equal.

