4.4.4 Additional Statistical Analyses

No additional analysis will be conducted.

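### The SAP's first primary test compares Baha 6 Max with Baha 5, not with unaided hearing, so the protocol's regulatory superiority question has no test in the SAP

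*SAP*

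**What the plan says.** **Protocol.** Section 6 lists speech in noise, Baha 6 Max against unaided hearing, as the first primary objective and labels it superiority. Section 7.1.1 gives the reason: "The primary purpose with this investigation is to test the Baha 6 Max SP versus unaided hearing in order to achieve regulatory approval". Section 9.3.1 sets the first primary comparison "between Baha 6 Max SP and unaided using a two-sided" paired Fisher permutation test at level 0.005. Section 9.6 repeats this for the FAS and adds the mean difference with a 99.5% CI. Baha 6 Max against Baha 5 on speech in noise is a secondary endpoint (sections 6 and 9.2.2). Section 9.1 gives confirmatory status to the p-values of the two primary analyses only.

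**SAP.** Section 4.1 keeps the protocol's label, "First primary analysis: Baha 6 Max SP vs unaided regard Adaptive speech in noise", and its sample-size paragraph. Section 4.2.2 then defines the first primary test differently: "The null-hypothesis that the proportion of responders for the Baha 6 Max SP and the Baha 5 SP are equal will be tested", by a binomial test. Section 4.2.1 calls this the primary objective and declares success if the two-sided p-value is below 5%. Section 4.2.3 applies the secondary tests "when testing the null-hypothesis that the Baha 6 Max SP and the Baha 5 SP are equal". The FAS definition in 4.3.1 names only the Baha 6 Max and Baha 5 periods. Section 4.4.4 closes with "No additional analysis will be conducted".

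**The concern.** A SAP may add detail to a protocol's primary analysis, but here it changes the comparator. Whether the new processor beats no device and whether it beats its predecessor are separate questions, and an answer to one does not settle the other. The protocol attaches the regulatory case to the first.

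An analyst who followed SAP 4.2 to 4.4 would produce no p-value or confidence interval against unaided hearing on any endpoint. Success would be judged on a device-to-device contrast that the protocol treats as secondary and descriptive. If the unaided comparison were added after the results were known, the claim it supports could be challenged as post hoc.

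**Working it through.** **1. The first primary analysis side by side**

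| Element | Protocol 9.3.1, 9.6 | SAP 4.1 | SAP 4.2.1, 4.2.2 |
|---|---|---|---|
| Comparator | Unaided | Unaided | Baha 5 |
| Variable | SNR in dB | SNR in dB | Responder yes/no |
| Test | Paired Fisher permutation | Paired Fisher permutation | Binomial |
| Two-sided level | 0.005, with Holm retest | 0.005 | 0.05 |

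The comparator changes in both 4.2.1 and 4.2.2, so it is not one stray word.

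**2. Is unaided hearing tested anywhere else in the SAP?**

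- Second primary test (4.2.2): preference, Baha 6 Max against Baha 5. This agrees with the protocol's hypotheses.
- Secondary tests (4.2.3): Baha 5 only. Protocol section 6 also plans sound-field thresholds and speech in quiet against unaided.
- Additional analyses (4.4.4): none.

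There is no such test. The data are planned for: protocol 7.3.3 to 7.3.5 schedule all three sound-booth tests unaided at Visit 3.

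**3. Does document versioning explain the switch?** SAP section 1 says it is based on CIP version 3.0. The protocol's change history lists only section 8.4 as changed in version 4.0. The statistical sections were therefore the same, and the SAP does not flag a change.

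**4. Which contrast does the sample size belong to?**

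Inputs (protocol 9.4, repeated in SAP 4.1): mean paired difference 16 dB, SD 12.5, two-sided alpha 0.005, 90% power, 15 subjects.

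Standardised effect: d = 16 / 12.5 = 1.28.

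Paired t power: P(|T| > t(0.9975; n−1)), with T noncentral t on n−1 degrees of freedom and noncentrality 1.28 × √n.

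| n | Noncentrality | Critical t | Power, paired t | Power, simulated permutation test |
|---|---|---|---|---|
| 14 | 4.789 | 3.372 | 89.2% | about 88% |
| 15 | 4.957 | 3.326 | 92.4% | about 91% |
| 16 | 5.120 | 3.286 | 94.7% | about 95% |

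The simulation draws normal differences and applies the exact sign-flip test (1,500 runs for n = 14 and 15, 800 for n = 16). Fifteen is the smallest n that reaches 90% by either method, so the plan's figure reproduces. The plain normal approximation, ((2.807 + 1.282) / 1.28)² = 10.2, rounds up to 11 and is too small at this sample size.

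**5. What supports the contrast the SAP tests?** The documents give no responder rates and no expected speech-in-noise difference between the two processors, so its power cannot be computed. If the test is run as an exact paired binomial test on discordant subjects (an assumption, since the SAP does not say), the smallest attainable two-sided p-value with m discordant subjects is 2 × 0.5^m:

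- m = 5: 0.0625
- m = 6: 0.031
- m = 9: 0.0039

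At least 6 of the 16 subjects would have to respond with one device and not the other, all in the same direction, to reach 5%. Reaching 0.005 would take at least 9.

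**The case against.** The strongest reply is that the unaided test is not really lost. The SAP describes itself as a companion to the CIP, protocol 9.6 still requires the test, SAP 4.1 still calls it the first primary analysis, and the per-protocol definition in SAP 4.3.2 still mentions three periods. On that reading, 4.4.4 does not exclude an analysis that is primary rather than additional. The remnants do show what was probably meant. They do not specify an analysis: SAP 4.1 justifies a sample size, while the hypotheses and the success rule stand in 4.2.1 and 4.2.2 and say something else. Protocol 9.11 assigns the detailed analyses to the SAP, and neither document says which prevails in a conflict. What stands is that the SAP contradicts itself as well as the protocol.

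Three narrower points are fair:

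- The 5% rule in SAP 4.2.1 has no direction. Read literally, a significant result in favour of Baha 5 would also count as success.
- The missing power basis has a second cause, the change from mean SNR to a responder rate.
- The loss on the secondary endpoints is descriptive, since protocol 9.1 gives those p-values no confirmatory role.

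None of these restores the unaided comparison.

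Protocol 9.3.1 has a slip of its own: it introduces the preference comparison as against unaided, although the hypotheses below it name Baha 5. That does not affect the first primary analysis.

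**Conclusion.** The concern holds. Followed as written, the SAP does not test superiority over unaided hearing. One of the two primary analyses and both secondary endpoints planned against unaided (sound-field thresholds and speech in quiet) have no test. The sample-size claim is sound for the protocol's contrast, with about 95% power at the planned 16 subjects, and gives no support to the contrast that replaced it. The power figures rest on the plan's own 16 dB and SD 12.5, with normal differences and no dropout. The conclusion about the comparator rests on the text alone. It concerns what is planned; the documents do not show which analysis was run. This must be fixed.

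**What to change.** - **SAP 4.2.1 and 4.2.2:** restore the protocol's first primary analysis. This is the within-subject SNR difference in dB, Baha 6 Max minus unaided, with a two-sided paired Fisher permutation test at 0.005 and the mean difference with 99.5% CI on the FAS. Delete the responder rule: the adaptive test returns the SNR in dB at which understanding is 50%, so an SNR of at least 50% is not a usable cut-off. Replace the single 5% success rule with the protocol's 0.005/0.045 split and Holm retest.
- **SAP 4.3.1:** put the unaided period back in the FAS definition, as in protocol 9.5.1.
- **SAP 4.2.3:** add paired Baha 6 Max against unaided analyses for sound-field thresholds and speech in quiet. Keep Baha 6 Max against Baha 5 on SNR as secondary.

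**Cost:** before database lock, SAP wording only. The sample size stands, and no new subjects, visits or measurements are needed. The documents give no lock date. The expected start was September 2020 with a total duration of 8 to 9 weeks, and this SAP version is dated 3 March 2021, so data collection may already have ended. If lock has passed, the protocol's analysis should still be run and the departure from the SAP reported in the Clinical Investigation Report, as SAP section 1 requires.
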